### **2.1.3 Efficacy endpoints**

Unless otherwise specified, all efficacy parameters values (scheduled or unscheduled) may be used to provide a value for the primary and secondary efficacy endpoints.

For FVC, FEV1 and FEV1/FVC parameters, a value is considered valid if this is an ATSBEST value with a grade “A” or “B” and a status “CLEAN” or “MANUAL”.

All measurements (scheduled or unscheduled) will be assigned to analysis windows defined in [Table 6](#), in order to provide an assessment of the efficacy parameter at each time point planned to be collected as per protocol. For all post-baseline time points, the value used for the analyses at a given time point (e.g at week 52) is the valid value obtained within the corresponding analysis window. If multiple valid values of a variable exist within an analysis window, the nearest from the targeted study day will be selected. In case of ties, the best value will be considered.

The baseline value is the last available and valid measurement obtained before or equal to the date and time of the first double-blind IMP injection. For patients randomized and not treated, the baseline value is defined as the last available and valid value obtained before or equal to the date and time of randomization.

#### **2.1.3.1 Primary efficacy endpoint(s)**

The pulmonary function test % predicted FVC is planned to be assessed at baseline, Week 12 (Visit 6), Week 24 (Visit 7), Week 36 (Visit 8), Week 52 (Visit 9/End of treatment) and Week 64 (Visit 10/End of study).

The primary efficacy endpoint of the study is the absolute change from baseline in % predicted FVC at 52 weeks in the mITT population.

#### **2.1.3.2 Secondary efficacy endpoint(s)**

##### *2.1.3.2.1 Key secondary efficacy endpoints*

Two key secondary endpoints will evaluate other aspects of the efficacy of SAR156597 in IPF:

- Patients experiencing Disease progression at 52 weeks in the mITT population
- Deaths (all-cause) at 52 weeks in the mITT population

##### *2.1.3.2.2 Disease progression endpoint*

Disease progression is defined as time from randomization to the first occurrence of any of the following events:

- decrease in absolute % predicted FVC $\geq$ 10% (as in [Section 2.1.3.1](#))
- decrease in absolute % predicted DLCO $\geq$ 15% (as in [Section 2.4.4.2.3](#))
- lung transplant (recorded on the dedicated e-CRF page during the study)
- death (recorded on the dedicated e-CRF page during the study)

Disease progression will be analyzed as a time-to-event variable: event date – randomization date + 1 day where the event date is described in [Table 2](#).

**Table 2 - Time-to-event variable definition for disease progression**

Scenarii	Event status	Event date
First event up to Day 375 is decrease in absolute % predicted FVC $\geq$ 10% or decrease in absolute % predicted DLCO $\geq$ 15%	event	Date of the 1 st decrease observed
First event up to Day 375 is death or lung transplant	event	Date of death or date of lung transplant
No event prior to last available and valid assessment of %predicted FVC or last available assessment of %predicted DLCO	censored	Min(date of last available %predicted FVC, date of last available %predicted DLCO)
No event up to Day 375 (last available and valid assessment of %predicted FVC and last available assessment of %predicted DLCO performed after Day 375)	censored	Date of Day 375

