11.4.2.2 Analyses of secondary efficacy endpoints

Disease progression, defined as decrease in absolute % predicted FVC $\geq 10\%$, or decrease in absolute % predicted DLCO $\geq 15\%$, or lung transplant, or death will be analyzed as a time to event variable. Patients not meeting the definition for disease progression will be considered censored at the time of their week 52 FVC assessment. For patients with a missing FVC assessment at week 52 the censoring time will be the time of the last measured FVC or DLCO assessment.

The time to disease progression will be compared between each active group and placebo using a log-rank test. The hazard ratio compared to placebo will be estimated from a Cox proportional hazards model.

The incidence of all-cause mortality will be calculated, but no hypothesis testing will be performed for this endpoint.

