			in efficacy analysis provided that the endpoint was measured or could be calculated (e.g. at least 1 baseline and 1 post-baseline values for imputing and calculating a change).
NA	NA	Baseline definition has been revised because the timeslot between a screening and a baseline value is large (up to 4 weeks) and there will not be several assessments at 52 weeks.	Last available value before first IMP administration.
NA	NA	%predicted DLCO analysis is of interest, it was missing in protocol.	Addition of the %predicted DLCO exploratory endpoint analysis.
NA	NA	
Primary efficacy endpoint - change in week 52 missing data (due to death or lung-transplant) imputation approach: the time-to-death or lung transplant approach is more sensitive in ranking patients. For example, a patient who dies early will be more penalized than a patient who dies lately during the study.
 
Primary efficacy endpoint - change in week 52 missing data (due to reasons other death or lung-transplant) imputation approach:
 
 
patients taking treatment at 52 weeks will be imputed using a linear regression run on their treatment arm completers.
 
patients not taking treatment at 52 weeks will be imputed using a linear regression run on the placebo completers.
 
	
Time-to-death or lung transplants will be used instead of allocating the lowest rank for all died and lung transplanted patients.
 
For patients with a week 52 missing data (due to reasons other than death or lung transplant), depending on treatment intake at 52 weeks, a linear regression will be performed on a particular set of completers.

NA	NA	Disease progression endpoint - change in analysis cut-off date: Day 375 will be used instead of superior boundary of week 52 analysis window (Day 406) in order to prevent from non-random censures.	Patients not meeting the definition for disease progression will be considered censored at the time of their week 52 FVC or DLCO assessment provided that it was performed before Day 375. For patients with a missing week 52 assessment, the censoring time will be the time of the last measured FVC or DLCO assessment. For patients with week 52 assessment performed after Day 375, the censoring time will be Day 375.

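### SAP Table 2 censors stable patients at the earlier of the last FVC and last DLCO but counts declines after that date as events, which slightly overstates Kaplan-Meier progression risk when the two dates differ

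*SAP*

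**What the plan says.** SAP 2.1.3.2.2 defines disease progression as time to the first of an FVC decline, a DLCO decline, lung transplant or death. Table 2 sets the dates.

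- **Row 1.** "First event up to Day 375 is decrease in absolute % predicted FVC" of at least 10%, or the DLCO equivalent of at least 15%: an event, dated at the first observed decline. The only time limit is Day 375.
- **Row 3.** No event before the last FVC or the last DLCO: censored at "Min(date of last available %predicted FVC, date of last available %predicted DLCO".
- **Row 4.** Censored at Day 375, but only with the "last available and valid assessment of %predicted FVC and last available assessment of %predicted DLCO performed after Day 375".

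Protocol 11.4.2.2 says a patient without progression is "censored at the time of their week 52 FVC assessment". If that FVC is missing, "the censoring time will be the time of the last measured FVC or DLCO assessment".

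SAP 1.5 (Table 1) revises the censoring of this endpoint. Such patients are "considered censored at the time of their week 52 FVC or DLCO assessment" if it was done before Day 375, otherwise at the last measured FVC or DLCO, or at Day 375 if the Week 52 test came later. It mentions no minimum. The stated aim of the Day 375 cut-off is "in order to prevent from non-random censures".

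**The concern.** Censoring should not depend on whether the patient later has the event. Under Table 2 read in row order, it does. Two patients with the same pattern of available tests get different follow-up: the one who declines on the remaining test stays at risk until the decline, and the one who stays stable is removed back at the earlier date. Observed event-free time is discarded selectively, so the risk set shrinks while the events stay, and the estimated progression risk rises.

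The two dates can differ for a documented reason. For FVC, "a value is considered valid if this is an ATSBEST value with a grade" of A or B and an accepted status (SAP 2.1.3), and no such filter is stated for DLCO. One post-baseline value of each test is enough to enter the analysis (SAP 2.4.4.2.1). At stake are the Kaplan-Meier event-free probabilities for a key secondary endpoint, which are reported by arm and by background-therapy status whatever the outcome of the testing hierarchy.

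**Working it through.** The documents give no progression rate, power figure or missing-test rate for this endpoint, so there is no planned figure to reproduce. The check has three parts.

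**1. Apply the rules to example patients** (target days from SAP Table 6).

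- Last DLCO on Day 169, valid FVC on Days 253 and 365. FVC decline on Day 365: event at Day 365. Stable: Table 2 censors at Day 169 and drops 365 − 169 = 196 observed days. The protocol censors at Day 365.
- Last valid FVC on Day 253, Week 52 FVC not valid, DLCO on Day 365. DLCO decline on Day 365: event. Stable: Table 2 censors at Day 253 and drops 365 − 253 = 112 days. Here the protocol fallback names the last FVC or DLCO without saying whether the earlier or the later is meant.

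In the first example a decliner also meets row 3's condition, because there was no event before the last DLCO. Rows 1 and 3 therefore overlap.

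**2. Size of the effect on the Kaplan-Meier risk.** Assumptions: true 52-week risk F = 30%; visits at Weeks 12, 24, 36 and 52 with a constant underlying hazard; a fraction f of patients with the last paired test at Week 36; a share v of later declines visible on the remaining test; test loss unrelated to progression.

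- Event-free at Week 36: S = 0.70^(36/52) = 0.7812.
- Week 52 visit hazard: h = 1 − 0.70^(16/52) = 0.1039.
- Table 2: risk = 1 − S × [1 − h(1 − f + fv)/(1 − f + fvh)].
- Same Min limit for declines (option a): risk = 1 − S(1 − h) = 30.0%.
- Later-date rule (option b): risk = 1 − S × [1 − h(1 − f + fv)].

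Worked case, f = 0.10 and v = 1, Table 2: the hazard becomes 0.1039/(0.90 + 0.10 × 0.1039) = 0.1142, and the risk 1 − 0.7812 × 0.8858 = 30.8%.

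| Visible share v | Table 2, f = 5 / 10 / 20% | Option (b), f = 5 / 10 / 20% |
|---|---|---|
| 100% | 30.4 / 30.8 / 31.8 | 30.0 / 30.0 / 30.0 |
| 70% | 30.3 / 30.6 / 31.3 | 29.9 / 29.8 / 29.5 |
| 50% | 30.2 / 30.4 / 30.9 | 29.8 / 29.6 / 29.2 |
| 30% | 30.1 / 30.2 / 30.5 | 29.7 / 29.4 / 28.9 |

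The Table 2 excess is 0.1 to 1.8 points, and zero when f = 0. As an upper-bound case, with 20% losing a test after Week 12, Table 2 gives 34.0% (all visible) or 32.0% (half visible). At a true risk of 20% or 40% (f = 10%, Week 36) it gives 20.6% or 41.0% (all visible). A separate simulation that modelled FVC, DLCO and death or transplant individually, with true risks near 28% and 39% and 5 to 20% losing one test after Week 12, 24 or 36, put the excess at 0.3 to 2.5 points.

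**3. Effect on the test.** Simulated identical arms, 100 per arm, F = 30%, unstratified log-rank at 1.96, 40,000 trials per setting, under Table 2:

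- Discordance 10% or 20% in both arms, Week 36: type I error about 5%.
- 20% versus 5%, Week 36: 5.2 to 5.3%, hazard ratio 1.03 to 1.05.
- 20% versus 5%, Week 12: 5.6% (half visible) to 7.0% (all visible), hazard ratio 1.06 to 1.12.

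**The case against.** **The Min date is defensible.** Event-free status on the composite is known only while both tests are known. That stands, but it supports Min only if declines after that date are also left out.

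**The fault may be wording, not a deliberate rule.** Row 3 overlaps row 1, so the author may not have intended the asymmetry. That stands as a reason to state the row order. It does not remove the problem, because reading row 1 first is the natural order.

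**The conflict with the protocol is narrow.** It is clear only for a Week 52 FVC with an earlier last DLCO. Both tests are scheduled at the same visits, patients off treatment are still asked back for both, and the one documented filter acts on FVC. With a missing Week 52 FVC, the protocol fallback can be read either way. This stands. It also stands that SAP 1.5 only summarises major changes, so the absence of Min there is a mismatch to tidy rather than a serious omission.

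**Stronger readings a reader might infer.** Both tests are repeated at Week 64, and the first database lock comes 4 weeks after the last Week 52 visit. One could infer that Week 64 tests count as last available and that censoring then depends on when a patient enrolled. The documents do not support this. SAP 3 limits the first analysis to data from the 52-week treatment period, protocol 11.5 limits it to endpoints up to Week 52, and SAP Table 1 explains the Day 375 row by a Week 52 test done late. Nor do they support the inference that the treatment comparison is materially biased: that needs discordance to differ by arm, and nothing indicates that it will.

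**Conclusion.** The point holds, at minor priority. Read in row order, Table 2 applies one follow-up limit to declines and a shorter one to stable patients, and the order of rows 1 and 3 is not stated. With 30% true progression and 5 to 20% discordance from Week 36, the Kaplan-Meier risk is overstated by about 0.1 to 1.8 points, and by about 4 points in the Week 12 upper-bound case. All these rates are assumptions. With no discordance there is no effect. Event counts do not change. The log-rank test and hazard ratio are essentially unchanged if discordance is similar across arms, and the endpoint is formally tested only if both doses succeed on the primary. The planned table of censoring reasons could reveal the problem but would not correct the estimate.

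**What to change.** In Table 2, apply one follow-up limit to FVC and DLCO declines and to censoring, and state which row takes precedence. Choose one:

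- **(a)** Keep Min, and do not count FVC or DLCO declines after it. This returns 30.0% throughout under the assumptions above, but discards about 0.1 to 1.6 observed declines per 100 patients (Week 36, 5 to 20% discordant; maximum 100 × 0.20 × 0.1039 × 0.7812 = 1.6).
- **(b)** Censor at the Week 52 FVC, otherwise at the later of the last valid FVC and the last DLCO, capped at Day 375. This is closest to the protocol, though choosing the later date is an interpretation and should be stated. It keeps every observed decline, but reads low when some declines would show only on the missing test. Its bias matches that of Table 2 in size at about 50% visibility and exceeds it below that.

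Deaths and transplants up to Day 375 remain events under both, so those occurring after the last test are still treated asymmetrically, as under the protocol rule. Make SAP 1.5 match Table 2, and report the other version as a sensitivity analysis. The cost is one or two table cells, one line in SAP 1.5 and one extra run.

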### 2.1.3.2.3 All-cause mortality endpoint

Deaths are reported during the study on the Death e-CRF page.

All-cause mortality endpoint will be analyzed as a time-to-event variable: event date - randomization date + 1 day where the event date is described in [Table 3](#).

**Table 3 - Time-to-event definition for all-cause mortality**

Scenarii	Event status	Event date
Death up to Day 375	event	date of death
Lung transplant	event	Date of transplant
Study discontinuation (according to EOS e-CRF page) before Day 375	censored	Min{max(date of last available information, SAE recovery date), date of Day 375}
No death up to Day 375	censored	Date of Day 375

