9.1.2 Secondary endpoints

Two key secondary endpoints will evaluate other aspects of the efficacy of SAR156597 in IPF:

- Patients experiencing Disease Progression as defined by the following events: decrease in absolute % predicted FVC ≥ 10 percent or decrease in absolute percent predicted DLCO ≥ 15 percent or lung transplant or death at 52 weeks
- Deaths (all cause) at 52 weeks

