##### *2.4.4.2.1 Disease progression endpoint*

The disease progression will be analyzed on the mITT population. Assessments at week 52 (performed before Day 375) will be used regardless of whether the patient has previously discontinued treatment. Only patients having a baseline and a post-baseline values in at least one time points analysis window for both the % predicted FVC and the % predicted DLCO parameters will be considered in the analysis. No week 52 missing data will be imputed for the disease progression.

The cumulative incidence of disease progression at 52 weeks will be presented graphically by treatment arm and background therapy status, using Kaplan-Meier method. The Kaplan Meier survival estimates (number of patients at risk, number of patients censored, number of disease progression events and probability of surviving without event (95% CI)) will be summarized by time points and overall (number of patients censored, number of events, median time to event).

The censoring reasons will be described by treatment arm and background therapy status.

The time to disease progression at 52 weeks will be tested comparing SAR156597 200 mg qw dose versus placebo using a log-rank test stratified on stratification factor (with/without Background Therapy) at a two-sided type I error level of 5%; and only if this comparison is significant will the SAR156597 200 mg q2w dose be tested versus placebo using a log-rank test stratified on stratification factor (with/without Background Therapy) at a two-sided type I error level of 5%.

The event rates for each of the 3 treatment arms, the hazard ratio and its 90 and 95% confidence interval (CI) compared to placebo for each active arm versus Placebo will be estimated from a

Cox model containing the treatment and the stratification factor variables. The underlying assumption of proportional hazards for Cox model will be checked by visual inspection.

In order to assess the significance, the magnitude and the repartition within components of the treatment effect of disease progression at 52 weeks, the following items will be described by treatment arm and by background therapy status:

- Summary of the disease progression at 52 weeks: number of events, event rates, p-values (only by treatment arm), estimated hazard ratios and their 90 and 95% CIs
- Description of each component as part of the disease progression: their number of events, event rates and their estimated hazard ratios

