#### 2.4.4.2.2 *All-cause mortality endpoint*

The all-cause mortality will be analyzed on the mITT population. Deaths from baseline to week 52 (performed before Day 375) will be used regardless of whether the patient has previously discontinued treatment.

The cumulative incidence of all-cause mortality will be presented graphically by treatment arm and background therapy status, using Kaplan-Meier method. The Kaplan Meier survival estimates (number of patients at risk, number of patients censored, number of death events and probability of surviving without event (95% CI)) will be summarized by time points and overall (number of patients censored, number of events, median time to event).

The censoring reasons will be described by treatment arm and background therapy status.

The event rates for each of the 3 treatment arms, the hazard ratio and its 90% and 95% CIs compared to placebo for each active arm versus Placebo will be estimated from a Cox model containing the treatment and the stratification factor variables. The underlying assumption of proportional hazards for Cox model will be checked by visual inspection.

No hypothesis testing will be performed as per protocol.

The same time-to-event analysis with IPF-related deaths only will be explored on the mITT population.

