Cumulative incidence of all-cause mortality	mITT	Kaplan-Meier representation and Hazard Ratio using a Cox model with treatment, stratification factor ,. No imputation.	No	No	IPF-related deaths: Kaplan-Meier representation and Hazard Ratio using a Cox model with treatment, stratification factor , stratification factor-by-treatment. No imputation.
Exploratory endpoints					
Change from baseline to week 52 in %predicted DLCO	mITT	MMRM with treatment arm, stratification factor, time point, treatment-by-time point interaction, stratification factor-by-treatment-by-time point interaction, % predicted DLCO baseline.No imputation.	No	No	No
Annual rate of acute IPF exacerbations	mITT	Annual rate from negative binomial model adjusted on stratification factor (with/without Background Therapy) and stratification factor-by-treatment interaction. No imputation.	No	No	No
Annual rates of respiratory and non-elective hospitalizations	mITT	Annual rates from negative binomial model adjusted on stratification factor (with/without Background Therapy) and stratification factor-by-treatment interaction. No imputation.	No	No	No
Change from baseline to week 52 in 6-MWT distance	mITT	MMRM with the fixed categorical effects of treatment arm, stratification factor, time point, treatment-by-time point interaction, stratification factor-by-treatment-by-time point interaction, supplemental oxygen use at baseline, 6-MWT distance at baseline. No imputation.	No	No	No

Endpoint	Analysis population	Primary analysis	Supportive analysis	Subgroup analysis	Other analyses
Change from baseline to week 52 in HRCT lung interstitial score (Total Fibrosing ILD score)	mITT	Ancova with baseline value, emphysema score at baseline, stratification factor, treatment, stratification factor-by-treatment interaction. No imputation.	No	No	No
Change from baseline to week 52 in SGRQ	mITT	MMRM with treatment arm, stratification factor, time point, treatment-by-time point interaction, stratification factor-by-treatment-by-time point interaction, SGRQ total score at baseline. No imputation.	No	No	No

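### SAP Table 3 counts lung transplant as an event in the all-cause mortality endpoint, so the estimates labelled mortality would be for death or transplant

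*SAP*

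**What the plan says.** Protocol section 9.1.2 lists as a key secondary endpoint "Deaths (all cause) at 52 weeks". SAP section 2.1.3.2.1 repeats it as "Deaths (all-cause) at 52 weeks in the mITT population", and Appendix B of the SAP summarises it as "Cumulative incidence of all-cause mortality".

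SAP section 2.1.3.2.3 makes this a time-to-event variable measured from randomization and takes the event date from Table 3. That table has four rows:

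- death up to Day 375: event, at the date of death;
- "Lung transplant event Date of transplant";
- study discontinuation before Day 375: censored;
- "No death up to Day 375": censored at Day 375.

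The analysis text in SAP section 2.4.4.2.2 refers only to deaths. Its Kaplan-Meier table is to show "number of death events and probability of surviving without event (95% CI". The section adds event rates and Cox hazard ratios with 90% and 95% confidence intervals, and plans no hypothesis test. It also repeats the same time-to-event analysis for IPF-related deaths.

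**The concern.** The row that drives the derivation does not match the endpoint's name or the analysis text. Someone programming from Table 3 produces a composite of death and transplant; someone programming from section 2.4.4.2.2 produces mortality. Either output would carry the mortality label.

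This is one of only two key secondary endpoints. According to the SAP's table of protocol changes (section 1.5), the Week 52 analysis informs the benefit/risk evaluation and the decision to move to Phase 3. SAP section 3 says the 52-week data will not be reanalyzed at the end of the study. A mislabelled mortality hazard ratio would therefore stand.

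**Working it through.** **Is the change declared?** SAP section 1.5 lists the departures from the protocol's statistical section. Its transplant entries concern ranking and imputation for the primary endpoint. None redefines mortality.

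**Where is transplant meant to count?** It is a named component of disease progression, where Table 2 limits it in time: "First event up to Day 375 is death or lung transplant". The transplant row in Table 3 has no such limit. Follow-up runs to Week 64, and the first database lock is 4 weeks after the last patient's Week 52 visit, so transplants after Day 375 in earlier-enrolled patients could already be in the database.

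**Patients run through Table 3:**

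| Patient | Rows that apply | Result |
|---|---|---|
| Transplanted by Day 375, alive at Day 375 | transplant; no death | event or censored |
| Transplanted, dies before Day 375 | transplant; death | event, two possible dates |
| First transplanted after Day 375, alive | transplant; no death | event after the cut-off, or censored at Day 375 |

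No order of precedence is given.

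**Does another output supply the missing estimate?** The missing-data and rank-quartile tables for the primary endpoint (SAP 2.4.4.1) and the death summaries (SAP 2.4.5.2) give counts and percentages. The disease progression analysis gives hazard ratios for death as an individual component, but its population is restricted: "Only patients having a baseline and a post-baseline values in at least one time points analysis window for both the % predicted FVC", and likewise for DLCO. A patient who dies before a first post-baseline test drops out. Table 3 is thus the only planned time-to-event estimate of death from any cause in the full mITT population.

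**Size.** The documents give no expected deaths or transplants, so there is no plan figure to reproduce. Assumptions: n = 100 per arm (the planned size), followed to Day 375; d deaths in each arm, so the true hazard ratio is 1.00; k transplants, all in one arm, in patients who survive to Day 375.

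- Reported cumulative incidence in that arm = (d + k)/n. With d = 5 and k = 0, 1, 2, 3: 5%, 6%, 7%, 8%, against a true 5%.
- Inflation of its reported deaths = k/d.
- Hazard ratio under proportional hazards = ln(1 − (d + k)/100) / ln(1 − d/100), inverted if the transplants are on placebo. For d = 5, k = 1: ln(0.94)/ln(0.95) = 0.0619/0.0513 = 1.21.

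| d | k | Inflation | HR, transplants on active | HR, transplants on placebo |
|---|---|---|---|---|
| 5 | 0 | 0% | 1.00 | 1.00 |
| 5 | 1 | 20% | 1.21 | 0.83 |
| 5 | 2 | 40% | 1.41 | 0.71 |
| 5 | 3 | 60% | 1.63 | 0.62 |
| 8 | 0 | 0% | 1.00 | 1.00 |
| 8 | 1 | 12.5% | 1.13 | 0.88 |
| 8 | 2 | 25% | 1.26 | 0.79 |
| 8 | 3 | 37.5% | 1.40 | 0.72 |

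For scale, the approximate 95% confidence interval with no transplants is exp(±1.96 × √(1/d + 1/d)):

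- d = 5: exp(±1.96 × 0.632) = 0.29 to 3.45;
- d = 8: exp(±1.96 × 0.5) = 0.38 to 2.66.

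Every shift in the table lies inside these intervals. An even split of transplants leaves the hazard ratio near 1.00.

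**The case against.** The strongest reply is that the analysis text already says deaths, so the plan is inconsistent rather than committed to a composite. Moreover, the SAP pairs transplant with death in several places, so the row may be deliberate. The last row of Table 3 can be read as residual: the discontinuation row already overlaps it, and a transplanted survivor would then simply be an event. The 52-week label arguably supplies the missing time limit. Protocol section 11.4.2.2 promises only the incidence of mortality, untested, and the death counts elsewhere come close to delivering it. Exclusion criterion E 09 should keep transplants few. The hazard ratios above depend wholly on assumed counts falling in one arm.

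Much of this stands as a limit on importance. The endpoint is descriptive, the size is assumed, and the residual reading is plausible. It does not remove the point. The deaths-only text is one side of the contradiction, and section 2.1.3.2.3 assigns the event date to Table 3. Even under the residual reading, a living patient is counted as a death, and the date for a patient who dies after transplant remains open. Where the SAP pairs the two outcomes in the primary analysis, it ranks transplant as better than death. E 09 covers listing within the next 6 months only, in a 52-week trial. Counts of deaths do not replace a full-mITT time-to-event estimate.

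**Conclusion.** The concern holds. Following Table 3 yields an estimate of death or lung transplant presented as all-cause mortality, with an event status or date left open for some transplanted patients. The IPF-related death analysis may inherit the ambiguity.

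The effect is zero without transplants. Under the assumptions above, 1 to 3 transplants confined to one arm inflate its reported deaths by 12.5% to 60% and move a true hazard ratio of 1.00 to between 0.62 and 1.63. Because no hypothesis is tested and the intervals are wide, this is a distorted label and point estimate and changes no test result. The primary endpoint, its type I error and its power are untouched. It is worth correcting before the first database lock because the endpoint is key secondary and the correction is small.

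**What to change.** - In Table 3, delete lung transplant as an event and count deaths only, up to Day 375.
- Keep transplanted patients at risk until death or the ordinary censoring date. Censoring at transplant can serve as a sensitivity analysis.
- If a death-or-transplant estimate is wanted, add it as a separate endpoint with that name, limited to Day 375.
- If any transplant row stays in Table 3, give it the Day 375 limit used in Table 2 and state which row takes precedence, including for a patient who dies after transplant.
- Apply the same rule to the IPF-related death analysis.

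The core change costs one table row and one line of derivation code, and possibly slightly fewer events in a descriptive endpoint. The sensitivity analysis and the separate composite, if adopted, each add one further run.
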